6.2 Analysis Sets

The intent-to-treat (ITT) analysis set is defined as all randomized subjects. This analysis set will be used for demographics and baseline characteristics, entrance criteria violations and other protocol deviations, study drug exposure and prior/concomitant medications summaries.

Since this is an exploratory study being conducted for the purpose of signal detection, the per protocol (PP) analysis set will be used for all efficacy summaries. This set is defined as all patients who completed at least 10 doses) of treatment, had a Day 8 PCSS assessment and no major protocol deviations.

The safety analysis set is defined as all subjects who received at least one dose of study drug. This analysis set will be used for all safety summaries, and subjects will be included in the treatment group which represents the treatment actually administered. If there are no errors in dosing (ie, each subject received the treatment to which he/she was randomized), it is anticipated that the safety analysis set will be the same as the ITT analysis set because it is expected that all randomized subjects will be dosed.

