Subjects will be both men and women, ages 18-60 years old, with a concussion resulting from a direct or indirect blow, rotation, or whiplash injury to the head or body. For the purposes of this study, we will define diagnosis of concussion/mTBI as those who have met the criteria set forth in this classification schema [23]:

Severity of Traumatic Brain Injury			
	GCS	PTA	LOC
Mild	13-15	<1 day	0-30 mins
Moderate	9-12	>1 to < 7 days	>30 mins to < 24 hrs
Severe	< 9	> 7 days	> 24 hrs

*GCS=Glasgow Coma Scale; PTA=Post-Traumatic Amnesia; LOC=Loss of Consciousness

However, as noted by the American Congress of Rehabilitation Medicine's statement on the definition of mTBI, "Due to the lack of medical emergency, or the realities of certain medical systems, some patients may not have the above factors medically documented in the acute stage. In such cases, it is appropriate to consider symptomatology that, when linked to a traumatic head injury, can suggest the existence of a mild traumatic brain injury [24]. When available, the study team will use medical records to confirm a patient's injury as an mTBI according to the schema above, however, if no records exist or are obtainable, clinical history and symptomatology will be used to confirm the diagnosis.

In Part A, subjects must be consented \leq 28 days post injury. In Part B, subjects must be consented, randomized, and start treatment within 24 hours of presentation to the Trauma Unit.

Subjects in both Part A and B will have a symptom severity score of ≥ 20 at the time of randomization in order to reduce the expected degree (number and severity) of spontaneous symptom resolution prior to study completion.

Subjects with pre-existing neurologic conditions other than mTBI (including cognitive dysfunction) will be excluded.

Subjects with concurrent long bone fractures or orbital fractures will be excluded.

Subjects receiving, or planning to receive, a continuous ketamine infusion while enrolled in study will be excluded.

Subjects with these known endocrinological abnormalities at baseline will be excluded from study: diabetes mellitus, excess or deficiency of growth hormone, cortisol, or prolactin. Exclusion from study for any other endocrinological abnormalities or diagnoses existing at baseline are ultimately up to the discretion of the study physician.

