In the event that subjects are enrolled by the Trauma team into Part B while having an inpatient status at TUKHS, the study team, Investigational Pharmacy, and the medical team will work together to dispense, store, and administer the study medication. The study team will continue to work with the Investigational Pharmacy and medical team, as appropriate, for the duration of the subject's inpatient status while on study, as necessary to comply with this protocol.

Attrition: This is a pilot study and no previous data exists as a basis to estimate attrition for this study. Any study participant who withdraws consent or is removed from Part A or Part B of the study during the 28-day trial period or does not successfully complete the protocol required 14 days of dosing may be replaced to allow for 40 subjects who complete the protocol.

Target Duration: The target duration of the treatment intervention with OXE-103 will be two weeks. The total involvement in the study including screening and follow up assessments will be 8 weeks.

Adverse Events: Oxeia, the supplier to the study team of the OXE-103 and placebo, performs and submits safety reports to the FDA under a separate IND. As OXE-103 has already undergone safety testing and the safety profile is known, the adverse events associated with OXE-103 are included in an Investigator's Brochure written by Oxeia Biopharmaceuticals. For the purposes of this study, the study team will collect all adverse events reported by subjects including SAEs and TEAEs regardless of suspected causality, and in accordance with appropriate rules and regulations. Study team will report any that are deemed by Investigator to be:

- Unexpected AND related
- Expected but occurring at an increased frequency or severity
- Occurring in such a way that changes the risks/benefit ratio to study participants and warrants an update in consent form and/or protocol.
- All SAE's will be reported per applicable rules and regulations (IRB/FDA)

Depression Screening: The study team will administer the PHQ-9 questionnaire at specified timepoints to help identify any potential risk or need for intervention.

Safety Monitoring: Subjects participating in Part A Arm 2 (non-treatment control) will not require safety monitoring. All other subjects participating in Part A Arm 1 and Part B Arms 1 & 2 will require safety monitoring.

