6.3 Subject Accountability

The number of subjects screened will be summarized along with the reasons for screen failure. The number (%) of subjects randomized, treated, completing treatment, completing study and in each analysis set will be summarized by treatment group. Reasons for not completing treatment and/or study will also be summarized by treatment group.

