6.4 Entrance Criteria Violations and Other Protocol Deviations

The number (%) of subjects randomized in violation of each entrance criterion (if any) will be summarized by treatment group. In addition, the number (%) of subjects for whom a pre-specified protocol deviation was observed will be summarized by treatment group.

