6.10 Missing Data Handling

For responder analyses, the last available post-baseline value will be used for patients who do not have an assessment on Day 15. No other data will be imputed.

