6.11 Visit Windows

Assessments during the treatment period (Days 4 to 15) that are not obtained on the scheduled day will be assigned to the nearest scheduled day. For example, a PCSS assessment performed on Day 12 will be assigned to Day 11 for the purposes of 'by visit' summaries, unless the assessment was inadvertently obtained in addition to the Day 11 assessment.

Assessments after the end of treatment that are not obtained within the scheduled window will be assigned to the nearest scheduled day (Day 21 or 44). For example, if the QOLIBRI assessment was not obtained until Day 25, it would still be assigned to Day 21 for the purposes of 'by visit' summaries.

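### Part B has no planned efficacy summary on all randomised subjects, and the per-protocol set used instead can drop a subject who has a Day 15 PCSS

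*SAP*

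**What the plan says.** SAP 6.2 defines the ITT set as everyone randomised, but uses it only for baseline characteristics, entry violations and deviations, drug exposure and medications. For efficacy, "the per protocol (PP) analysis set will be used for all efficacy summaries". The reason given is that the study is exploratory and looks for a signal. To enter the per-protocol (PP) set a subject must have taken at least 10 doses, "had a Day 8 PCSS assessment and no major protocol deviations".

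A Day 15 PCSS is not a condition, although the three responder measures in SAP 5.1 are assessed at Day 15. Two further rules matter:

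- SAP 6.10, for responder analyses: "the last available post-baseline value will be used for patients who do not have an assessment on Day 15".
- SAP 6.11, for treatment-period assessments: those "that are not obtained on the scheduled day will be assigned to the nearest scheduled day".

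SAP 6.8 adds no efficacy summary on another set. The protocol's Statistical Analysis section names no analysis set, and SAP section 1 gives the SAP precedence where the two differ.

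The protocol (General study design) makes Part B randomised, double-blind and placebo-controlled, with up to 50 enrolled to obtain 20 completers per arm. Under Attrition, a participant who "does not successfully complete the protocol required 14 days of dosing may be replaced to allow for 40 subjects who complete the protocol".

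On accountability, SAP 6.3 gives the number in each analysis set by group, and adds: "Reasons for not completing treatment and/or study will also be summarized by treatment group". SAP 6.4 counts subjects "for whom a pre-specified protocol deviation was observed will be summarized by treatment group", and SAP 6.6 tabulates doses taken.

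**The concern.** All three PP conditions depend, or can depend, on events after randomisation, and those events may be related to tolerability or recovery. Restricting every efficacy summary to subjects who meet them gives up the balance that randomisation provides, in the one part of the current protocol that is still randomised.

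The conditions also do not match the endpoint. A subject with an observed Day 15 score is lost if the Day 8 PCSS was skipped or a deviation is called major. A subject with no Day 15 score stays in, represented by a Day 8 or Day 11 value.

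The study is descriptive, so no type I error is at stake. What is at stake is the use of the estimates. SAP 6.1 intends them for power calculations and endpoint definition, and SAP 6.8 uses them in an ROC analysis to choose the improvement threshold that best separates the arms. Any selection effect would pass into later designs. SAP 6.3, 6.4 and 6.6 show how many subjects were excluded and why, but not how those subjects fared. The only individual listings planned (SAP 6.9) are for serious adverse events and adverse events leading to discontinuation.

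**Working it through.** The plan states no power, effect size or dropout rate, so there is no figure to reproduce. The check has three steps.

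**1. How a subject with a Day 15 PCSS can be excluded**

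- *No Day 8 PCSS.* The scheduled days are 4, 8, 11 and 15. Under the nearest-day rule, Days 7, 8 and 9 map to Day 8; Day 10 maps to Day 11 (1 day away against 2); Day 6 is a tie between Days 4 and 8. Only a skipped assessment, or one as late as Day 10, clearly fails. This should be uncommon.
- *Fewer than 10 doses.* Planned doses are 2 × 14 = 28, so the threshold is 10/28 = 36%, reached at the end of Day 5 with full twice-daily dosing. Day 15 data then exist only if the subject is followed after stopping. The protocol does not state this; it says only that such subjects may be replaced.
- *Major deviation.* Neither document defines the term, so this route cannot be sized.

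**2. How far the responder difference can move**

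Assumptions: n = 25 randomised per arm (the Part B maximum of 50, split 1:1), k excluded per arm, outcomes of the excluded known. Let d be PP responders on OXE-103 minus PP responders on placebo, and a and b the responders among those excluded from each arm (0 to k).

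- PP difference = d / (25 − k)
- All-randomised difference = (d + a − b) / 25

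| k per arm | d | PP difference | All-randomised range | Largest shift from PP |
|---|---|---|---|---|
| 1 | 5 | 5/24 = 20.8 points | 4/25 to 6/25 = 16 to 24 | 20.8 − 16 = 4.8 |
| 2 | 5 | 5/23 = 21.7 points | 3/25 to 7/25 = 12 to 28 | 21.7 − 12 = 9.7 |
| 5 | 4 | 4/20 = 20.0 points | −1/25 to 9/25 = −4 to 36 | 20 − (−4) = 24 |

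Example for k = 1: PP gives 17/24 against 12/24. All randomised gives 17/25 against 13/25 = 16 points if only the excluded placebo subject responded, or 18/25 against 12/25 = 24 points if only the excluded OXE-103 subject did.

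The k = 5 row is an extreme case. It supposes that all 50 − 40 = 10 places above the completer target fail PP, although a non-completer with 10 or more doses can remain in the set.

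One-sided exclusion with no true effect: take 15/25 = 60% response in both arms and exclude only OXE-103 non-responders. The PP rate on OXE-103 becomes 15/24 = 62.5%, 15/23 = 65.2% or 15/20 = 75% with 1, 2 or 5 excluded. The spurious difference is 2.5, 5.2 or 15.0 points. Excluding only placebo non-responders reverses the sign.

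**3. Comparison with sampling error**

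95% half-width = 1.96 × √(2p(1 − p)/25), with p assumed:

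- p = 0.6: 27.2 points
- p = 0.5: 27.7 points
- p = 0.7: 25.4 points

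Every shift in the table is below these values.

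**The case against.** The choice is deliberate and explained, in a study that both documents call unpowered and descriptive. The 10-dose threshold is lenient. The Day 8 condition is weaker than it looks: subjects receive an 8-day supply and collect the rest at the Day 8 visit, and the schedule footnote puts that day's questionnaires before dispensing. A subject who continues treatment should therefore have a Day 8 PCSS. SAP 6.14 defers unblinding until the database for the part is locked, which limits treatment-aware exclusions. A reader could compute best-case and worst-case bounds for the responder result from the counts in SAP 6.3. Finally, an all-randomised summary brings in more carried-forward early values, in a condition where the protocol expects spontaneous recovery: it requires a symptom score of at least 20 "in order to reduce the expected degree (number and severity) of spontaneous symptom resolution prior to study completion".

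Much of this stands. Exclusions may be few, and selection is the smaller uncertainty in every case calculated. It does not justify leaving the other result out:

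- Looking for a signal is a reason to show a PP result, not a reason to omit the all-randomised one.
- Blinded review does not remove tolerability-driven dropout, and SAP 6.14 does not say that PP membership is fixed before unblinding.
- Bounds computed from counts are wider than a result computed from outcomes that were collected.
- The carried-forward problem is real, but it can be disclosed and tested.

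**Conclusion.** The concern holds. No efficacy result on all randomised Part B subjects is planned in either document, and the PP rule can remove subjects with the outcome of interest while keeping others on carried-forward values. The reading of the text is firm; the size is not, because the documents give no exclusion rate.

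On the assumptions above, one or two exclusions per arm can move the responder difference by up to about 5 or 10 points in either direction. The bias is zero if nobody is excluded. The bounds also need the outcomes of excluded subjects to exist, which is uncertain for those who stop drug early. This does not invalidate the study. It is a worthwhile, inexpensive improvement, because the dependence on selection, unlike sampling error, can be shown from whatever data were collected on the excluded subjects.

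**What to change.** Revise SAP 6.2, with a line each in 6.8 and 6.10, before Part B is unblinded:

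- Summarise Part B responders, change scores and the ROC analysis on all randomised subjects with a baseline PCSS, by assigned arm, using all available post-baseline data.
- Show the PP results beside them as supportive.
- Keep the SAP 6.10 rule for responders, but report per arm how many subjects have no post-baseline PCSS and how many Day 15 values are carried forward, by source day. Under PP every carried value comes from Day 8 or later; in the wider set a Day 4 score could stand as the Day 15 outcome.
- Add one sensitivity analysis that counts subjects without a Day 15 value as non-responders.

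The cost is a revised paragraph, two short additions and some repeated tables on a set the SAP already defines. No visits or subjects are added; for those who stop drug early, the summary uses whatever was collected. The SAP needs updating in any case: version 1.0 (November 2020) still describes Part A as randomised against placebo, whereas the March 2021 protocol makes it open-label with a non-treatment control. The drawbacks are more early values carried forward than under PP, and an estimated effect that may change in either direction.

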6.3 Subject Accountability

The number of subjects screened will be summarized along with the reasons for screen failure. The number (%) of subjects randomized, treated, completing treatment, completing study and in each analysis set will be summarized by treatment group. Reasons for not completing treatment and/or study will also be summarized by treatment group.

6.4 Entrance Criteria Violations and Other Protocol Deviations

The number (%) of subjects randomized in violation of each entrance criterion (if any) will be summarized by treatment group. In addition, the number (%) of subjects for whom a pre-specified protocol deviation was observed will be summarized by treatment group.

6.5 Demographic and Baseline Characteristics

Age at randomization, sex, race, ethnicity and days since injury will be summarized with appropriate statistics for each treatment group. Days since injury will be calculated as randomization date – injury date. Age and days since injury will also be summarized categorically (Age: 18-25, 26-35, 36-45 and 46-55 years; Days since injury: ≤7, 8-14, 15-21, 22-28, >28 days).

Medical history/concurrent conditions will be summarized for each treatment group by International Classification of Diseases, Tenth Revision, Clinical Modification (ICD-10-CM) diagnoses obtained from BioPortal [1,2]. In this summary, a subject may be counted only once for each distinct diagnosis.

6.6 Study Drug Exposure

The total number of doses self-administered by each subject will be summarized as both a continuous and categorical (≤7, 8-14, 15-21, 22-28 doses) variable and presented for each treatment group.

6.7 Prior and Concomitant Medications

A prior medication is defined as any medication reported in use by the patient prior to randomization. A concomitant medication is defined as any medication either in use at randomization which was allowed to be continued during the treatment period, or, one that is started post-randomization and prior to the end of study. One medication report may be identified as both a prior and a concomitant medication.

Prior and concomitant medications will be summarized for each treatment group by generic name as determined by RxNORM ontology in BioPortal. In these summaries, a subject may be counted only once for each unique medication.

6.8 Efficacy Analysis

As described previously, binary variables (responders) and continuous variables (values and changes from baseline) will be summarized with appropriate descriptive statistics for each treatment group and each visit (as needed). Changes from baseline over time will also be presented graphically with means (95% confidence intervals) with both treatment groups presented on the same figure.

To evaluate the appropriateness of the current responder definitions, a Receiver Operating Characteristic (ROC) analysis will be performed for each response outcome measure. The current definitions indicate that a ≥20% improvement over baseline is required for a subject to be considered a responder. In the ROC analysis, the percent improvement will be varied from 5% to 95% to determine which percentage is best for distinguishing OXE-103 treated subjects from placebo subjects. If data suggest an early treatment response, the ROC analysis may be performed for a time point earlier than Day 15.

FDA pre-IND guidance from the FDA on the clinical development of OXE-103 advised that “***The outcome measure should be constructed in a way that ensures that a score change is indicative of a meaningful improvement in how a patient feels or functions that comes from a treatment effect specific to mild TBI.***” Pearson and Spearman correlation coefficients (and p-values) will be calculated to examine

relationships between the PCSS changes and changes in the quality of life measures (QOLIBRI total score and PGAS VAS).

Relationships between PCSS changes and changes in cognition and balance (BrainCheck composite measure) will also be examined using correlation coefficients.

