We propose a pilot study to treat 1) Sub-acute concussion with OXE-103 in Part A and 2) Acute concussion management with OXE-103 within 24 hours of presentation to the Trauma Unit in Part B. For Part A, we will recruit subjects from the University of Kansas Health System Center for Concussion Management (CCM) clinics which include Neurology, Sports Medicine, and Neurosurgery/PM&R. For Part B, we will recruit subjects from the University of Kansas Health System Trauma Unit. In Part A we will compare an open-label treatment arm (OXE-103) to a non-treatment concurrent control arm. Part B will be randomized double blind 1:1 to treatment with OXE-103 and placebo. We will compare these using self-report symptom scoring, quality of life questionnaires, computerized cognitive testing assessing executive function, memory and processing speed, and accelerometer-based balance scoring. The exploratory nature of this study is not powered to yield statistically significant outcomes, but will allow detection of trends within subjects and between groups, will support comparison with standard tests of neurocognitive functions, and will provide sample size estimates for future studies of people with persistent concussion related symptoms.

This study is highly relevant clinically and uniquely suited to being conducted at the CCM. It will be the first to test ghrelin as therapy for sub-acute concussion.

Specific Aims:

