Outcomes for the investigation of the effect of OXE-103 will be based on self-reported symptom scoring, quality of life questionnaires, computerized cognitive testing assessing executive function, memory and processing speed, and accelerometer-based balance scoring. Safety assessments will include collection of adverse events, clinical laboratory samples, electrocardiograms (ECGs), vital signs including body weights, suicide screening and physical/neurological examination findings.

3. Study Objectives

The primary objective of this study is to describe the change in symptom burden of subacute or acute concussion for the two treatment groups in each part, as measured by the change from baseline to Day 15 in the Post-Concussion Symptom Score questionnaire (PCSS) total score, total number of symptoms and total score for the 4 most bothersome symptoms (4MBS, as identified on Day 1). Improvements of $\geq 20\%$ will be considered clinically meaningful.

The secondary objectives are to:

- Describe the change in quality of life for the two groups in each part as measured by the change from baseline to Day 15 in the Quality of Life after Brain Injury (QOLIBRI) total score and Patient Global Assessment of Status Visual Analog Scale (PGAS VAS).
- Describe changes in cognitive performance for the two groups in each part as measured by the change from baseline to Day 15 in the BrainCheck composite score.

Exploratory objectives of the study are to:

- Describe the correlation between the change in symptom burden and quality of life during the treatment period for each group in each part.
- Describe changes in symptom burden and quality of life at different time points for the two groups in each part.

4. Sample Size

The exploratory nature of this study is such that it is not powered to yield statistically significant outcomes, but will allow detection of trends within subjects and between groups within each part, will support comparison with standard tests of neurocognitive functions, and will provide sample size estimates for future studies of individuals with acute or persistent concussion related symptoms.

The study will enroll a maximum of 50 subjects in each part, but may stop recruiting if each group has at least 20 participants who have completed the study.

5. Outcome Measures

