5.1 Primary Efficacy Outcome Measures

- PCSS severity responder as defined by $\geq 20\%$ improvement over baseline at Day 15 in the severity score
- PCSS symptom responder as defined by $\geq 20\%$ improvement over baseline at Day 15 in the number of symptoms
- PCSS 4MBS responder as defined by $\geq 20\%$ improvement over baseline at Day 15 in the 4MBS severity score
- Change from baseline in PCSS severity score at each post-baseline assessment (Days 4, 8, 11, 15, 21 and 44)
- Change from baseline in PCSS number of symptoms at each post-baseline assessment (Days 4, 8, 11, 15, 21 and 44)
- Change from baseline in PCSS 4MBS severity score at each post-baseline assessment (Days 4, 8, 11, 15, 21 and 44)

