6.1 General Methods

This pilot study will describe changes observed in the two treatment groups, placebo versus OXE-103, separately for each part. Since the study is exploratory, analyses will focus on descriptive comparative statistics and not on a pre-specified statistically significant primary endpoint. Data will be used to enable power calculations and the definition of suitable clinical endpoints for further clinical development. Data from baseline and on Study Days 4, 8, 11, 15, 21, and 44 will be analyzed. Note that day definitions in this study will follow the Clinical Data Interchange Standards Consortium in that there is no Day 0;

assessments performed prior to randomization will be done on Days -7 and -3 (Part A only) and randomization is considered Day 1.

For all evaluations of changes from baseline, baseline is defined as the last reported value before the first dose of study drug. In most instances, this will be the value recorded on Day 1.

For the evaluation of safety, a treatment-emergent finding is any result that is newly reported after the first dose of study drug. This may include an existing condition which worsens in severity after the start of treatment.

Continuous variables such as total score or change from baseline will be summarized by the number of observations, mean, standard deviation, median, minimum and maximum value. Graphs of changes from baseline over time will present the means and 95% confidence intervals.

Binary or categorical variables will be summarized by the number of observations in each category along with the percent of observations.

To aid in interpretation of the importance of relationships, correlation coefficients (Pearson and Spearman) will be reported with p-values.

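### SAP 6.8 tests the 20% responder cut-off only by how well a cut-off separates the arms; this cannot show meaning to patients and, under the usual meanings of 'best', overstates the arm gap

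*SAP*

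**What the plan says.** SAP 5.1 lists three responder measures at Day 15, each requiring at least 20% improvement: PCSS severity ("improvement over baseline at Day 15 in the severity score"), number of symptoms, and the four most bothersome symptoms (4MBS). SAP 6.8 then plans a check on that 20%: "To evaluate the appropriateness of the current responder definitions, a Receiver Operating Characteristic (ROC) analysis will be performed for each response outcome measure". The method is that "the percent improvement will be varied from 5% to 95% to determine which percentage is best for distinguishing OXE-103 treated subjects from placebo subjects". It adds: "If data suggest an early treatment response, the ROC analysis may be performed for a time point earlier than Day 15". No criterion for 'best', step size, tie rule or correction for the search is given.

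The next paragraph of SAP 6.8 cites FDA advice that a score change should indicate "meaningful improvement in how a patient feels or functions that comes from a treatment effect specific to mild TBI". The method attached to it is Pearson and Spearman correlation of PCSS change with change in QOLIBRI and PGAS. The protocol's Statistical Analysis section also compares improvement on those scales with responder status, but gives no method. On use of the results, SAP 6.1 says "Data will be used to enable power calculations and the definition of suitable clinical endpoints for further clinical development", and SAP 4 says the study "will provide sample size estimates for future studies of individuals with acute or persistent concussion related symptoms".

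**The concern.** A responder cut-off is appropriate if patients who pass it have improved in a way they would recognise. An ROC can address that when its reference state is a patient-rated improvement. Here the reference state is the arm. The FDA sentence has two halves, a meaningful improvement and a treatment effect, and arm separation bears only on the second.

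There is also a selection problem. If 'best' means the largest separation, the cut-off is tuned to whatever gap chance produced in about 40 subjects, and the gap then reported at that cut-off is too large. Moving to an earlier day because the data suggest a response adds a second data-driven choice.

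At stake is the study's stated product: endpoint definitions and inputs for sizing later trials.

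**Working it through.** **Part 1. What the planned analyses can establish**

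| Analysis | Reference | Yields a cut-off? |
|---|---|---|
| ROC over 5% to 95% (SAP 6.8) | Treatment arm | Yes |
| Correlations with QOLIBRI and PGAS (SAP 6.8) | Patient-rated change | No |
| Responder status against QOLIBRI and PGAS (protocol, Statistical Analysis) | Patient-rated change | No; takes the cut-off as given |

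The only search for a cut-off is the arm-based one. Its answer follows where the scores lie. With the same assumed 15-point benefit and SD 35, the median Youden cut-off is 40%, 55% or 75% when the control mean is 30%, 50% or 70%. The benefit is identical in all three cases.

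**Part 2. What three common rules do**

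Let S be the responder rate on OXE-103 and F the rate on placebo at a given cut-off. Then sensitivity = S and specificity = 1 − F.

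- Maximum Youden: S + (1 − F) − 1 = S − F. This is the arm gap itself, so the rule picks the largest observed gap.
- Closest to the corner: minimise (1 − S)² + F². This also rewards a large S − F.
- Sensitivity = specificity: minimise |S − (1 − F)| = |S + F − 1|. This depends on the sum of the rates, not their difference. It lands near the pooled median.

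**Inputs**

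- From the documents: 20 completers per arm (SAP 4; protocol, Specific Aim 1), 1:1 allocation in Part B, cut-offs 5% to 95%.
- Assumed, because the documents give no distribution: percent improvement Normal(50, 40) capped at 100, steps of 5, ties broken at random, one outcome, Day 15 only.
- 40,000 simulated trials per setting. The documents state no power or effect size, so there is no figure of the plan's to reproduce.

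**Results** (points of responder rate)

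| Rule | No effect: mean gap shown (true 0) | No effect: share of trials with gap ≥ 20 | 15-point shift: shown v true |
|---|---|---|---|
| Youden | 14.6 | 38% | 26.8 v 12.7 |
| Closest to corner | 11.2 | 31% | 24.4 v 14.1 |
| Sensitivity = specificity | about 0 (−0.1) | 14% | 15.1 v 14.6 |
| Fixed 20% | 0 | 9% | 9.6 v 9.6 |

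Hand check of the last cell: Φ((65 − 20)/40) − Φ((50 − 20)/40) = Φ(1.125) − Φ(0.75) = 0.870 − 0.773 = 0.096.

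Overstatement at the shift: 26.8 − 12.7 = 14.1 (Youden), 24.4 − 14.1 = 10.3 (corner), 15.1 − 14.6 = 0.5 (sensitivity = specificity).

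With control means of 30 to 70, the no-effect gap stays at 14 to 15 (Youden), about 11 (corner) and 0 (sensitivity = specificity).

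**Part 3. An arm-blind anchor for comparison**

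Give PGAS percent change the same assumed distribution, with correlation 0.5 or 0.7 to PCSS change. With no effect, the arm gap at the anchor-derived cut-off averages 0. With the 15-point shift it shows 13.2 to 13.9 against 12.5 to 13.0 true.

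**The case against.** The strongest reply is that SAP 6.8 never says the ROC demonstrates patient benefit. The FDA sentence opens a separate paragraph with its own method, the correlations. The study is exploratory, descriptive and unpowered, the 20% responder rates remain listed outcomes, and the ROC's stated output is a percentage, not an effect estimate. All of this stands, and it limits the point. What remains is that the appropriateness of the 20% is judged by arm separation alone, and no analysis derives a cut-off from patient ratings.

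Three stronger readings are tempting and should not be drawn.

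- *The gap is inflated whatever 'best' means.* It is not: sensitivity = specificity gives essentially no inflation. The size of the bias depends on a rule that the SAP leaves open.
- *A later trial will be undersized.* No section says that the selected cut-off or its rates will be used for sizing. SAP 4 and 6.1 refer to the study's data in general.
- *The search would nearly always reject 20% by chance.* With no effect, Youden picks 20% in about 5% of trials, which is simply 1 in 19 grid points. Under closest-to-corner the share depends on the assumed mean: about 11% at mean 30 and 0.1% at mean 70. This says little about the plan.

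The search also has some merit. Under the assumed shift, the true gap is larger at 50% (14.6 points) than at 20% (9.6), so a more sensitive cut-off may exist. The objection to using PGAS as an anchor stands in part too. PGAS asks about the effect of symptoms, so it is not independent of PCSS, and the protocol gives no derivation for its 20% threshold.

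**Conclusion.** The point holds in limited form. That arm separation cannot establish meaning to patients follows from the design of the ROC and needs no simulation. The overstatement of the arm gap is conditional on the rule: about 15 points (Youden) or 11 points (closest-to-corner) with no effect, about 14 or 10 with a true 15-point shift, and close to zero under sensitivity = specificity. These sizes rest on 20 per arm and an assumed score distribution. The direction for Youden and closest-to-corner was the same in every distribution tried.

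The prespecified 20% responder rates and continuous changes in SAP 5.1 are untouched. Harm arises only if the selected cut-off or its rates go into the endpoint definition and power calculations named in SAP 4 and 6.1. The change should be made, but the planned main results do not depend on it.

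**What to change.** 1. Add one anchor-based Day 15 ROC for each PCSS responder measure (severity, symptom count, 4MBS), by part, pooled over arms with arm labels removed, and run before that part is unblinded under SAP 6.14. Part A is open-label, so there the protection is removing the labels and fixing the rules in advance. Main anchor: a PGAS fall of at least 20%, the protocol's own threshold. Sensitivity anchor: QOLIBRI improvement of at least 20%, with scoring direction stated. Name the analysis set (SAP 6.2 uses the per-protocol set for efficacy), the handling of missing Day 15 PGAS (the carry-forward in SAP 6.10 covers responder analyses only) and of near-zero baseline PGAS, and the selection and tie rule. Give a bootstrap confidence interval.
2. Report the between-arm responder difference at the prespecified 20% as the main result, and at the anchor-derived cut-off as supportive.
3. If the arm-based search is kept, define 'best' and a tie rule, fix it at Day 15, label it hypothesis-generating, and do not use its responder rates for sizing. Limit it to Part B, because under the current protocol Part A has no placebo group: "In Part A we will compare an open-label treatment arm (OXE-103) to a non-treatment concurrent control arm".

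Cost: SAP wording and a little more analysis. PGAS and QOLIBRI are already scheduled on every PCSS day in all arms. The anchor cut-off will be imprecise. With 40 subjects and an assumed correlation of 0.5, its 10th to 90th percentile range is 15% to 65% (Youden) or 20% to 55% (corner). Only about 9 of 40 would be non-improvers on the anchor (40 × Φ((20 − 50)/40) = 40 × 0.227). It may therefore neither confirm nor reject 20%, it rests on a PGAS threshold that the protocol does not derive, and it may show a smaller drug-placebo gap than the arm-based search.
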